#### **4.5.2. Adverse Events**

Adverse events analyses including the analysis of adverse events (AEs), Serious AEs (SAEs) and other significant AEs will be based on GSK Core Data Standards.

An overview summary of AEs, including counts and percentages of participants with any AE, AEs related to study intervention, Grade 3 and 4 AEs, Grade 3 and 4 AEs related to study intervention, AEs leading to permanent discontinuation of study intervention, study intervention related AEs leading to permanent discontinuation of study intervention, AE leading to dose reductions, AEs leading to dose delays, SAEs, SAEs related to study intervention, fatal SAEs, and fatal SAEs related to study intervention will be produced. Unless otherwise specified, AEs will be summarized by treatment arms. AEs related to pomalidomide and dexamethasone separately, OR pomalidomide and dexamethasone in combo will all be considered as AEs related to the pom/dex regimen and summarized under the pom/dex treatment arm. Adverse events will be coded using the standard Medical Dictionary for Regulatory Affairs (MedDRA dictionary) and graded by the investigator according to the NCI-CTCAE, (version 5.0).

A summary of number and percentage of participants with any adverse events by maximum grade will be produced. AEs will be sorted by Preferred term (PT) in descending order. The summary will use the following algorithms for counting the participant:

- **Preferred term row:** Participants experiencing the same AE preferred term several times with different grades will only be counted once with the maximum grade.
- **Any event row:** Each participant with at least one adverse event will be counted only once at the maximum grade no matter how many events they have.

The frequency and percentage of AEs (all grades) will be summarized and displayed in two ways: 1) in descending order by PT only and 2) in descending order by SOC and PT. In the SOC row, the number of participants with multiple events under the same SOC will be counted once.

A summary of number and percentage of participants with treatment-emergent AEs by maximum grade will be also produced.

A separate summary will be provided for study intervention-related AEs. A study intervention-related AE is defined as an AE for which the investigator classifies the possible relationship to study intervention as “Yes”. A worst-case scenario approach will be taken to handle missing relatedness data, i.e. the summary table will include events with the relationship to study intervention as ‘Yes’ or missing. The summary table will be displayed in two ways: 1) by maximum grade sorted by PT in descending order and 2) in descending order by SOC and PT.

A summary of cumulative incidence of AE by number of cycles (<=1, <=2, <=4, <=6, <=8, <=10, Any) received at first occurrence will be provided.

In addition, AEs of maximum grade of 3 or higher will be summarized separately by PT.

All SAEs will be tabulated based on the number and percentage of participants who experienced the event. Separate summaries will also be provided for study intervention-related SAEs. The summary tables will be displayed by PT. The summary of all SAEs will also be created by SOC and PT. In addition, a summary of cumulative incidence of SAE by number of cycles (<=1, <=2, <=4, <=6, <=8, <=10, Any) received at first occurrence will be provided.

A study intervention-related SAE is defined as an SAE for which the investigator classifies the relationship to study intervention as “Yes”. A worst-case scenario approach will be taken to handle missing data, i.e. the summary table will include events with the relationship to study intervention as ‘Yes’ or missing.

A summary of non-serious AEs that occurred in 5% of the participants or above will be provided (no rounding for the percentage will be used in terms of 5% threshold, e.g., event with 4.9% incidence rate should not be included in this table). The summary will be displayed by SOC and PT.

All AEs will be listed. Additionally, a listing of subject IDs for each individual AE will be produced. Separate supportive listings with participant-level details will be generated for fatal and non-fatal SAEs, respectively. The relationship between MedDRA SOC, PT, and Verbatim Text will be listed.

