
Design Features
	
 
• This study is a Phase III, open-label, randomized, multicenter study evaluating the efficacy and safety of single agent belantamab mafodotin compared to pom/dex in participants with RRMM.
 
• The study will include a screening period, study treatment period, and follow-up.                         
 
○ During Screening, participants will be evaluated for study eligibility per protocol as defined in the Inclusion/Exclusion criteria (see Section 6 of Protocol Amendment 3). Eligible participants must have been previously treated with at least two prior lines of therapy, including at least 2 consecutive cycles of lenalidomide and a proteasome inhibitor (PI), (given separately or in combination) and must have documented progression (a) on, or within 60 days of completion of the last therapy or (b) must be non-responsive while on last treatment, where non-responsive is defined as not achieving at least Minimal Response (MR) after 2 complete treatment cycles. In such cases lack of achieving of MR must be determined no earlier than at least 4 weeks after the last treatment.
 
○ Following Screening, approximately 320 participants will be centrally randomized in a 2:1 ratio to either Arm 1 (single agent belantamab mafodotin) or Arm 2 (pom/dex), as described in Section 1.1 of Protocol Amendment 3. Participants will be stratified based on the following: previous treatment with anti-CD38 (Y/N), with a 40% global enrolment cap for participants with prior anti-CD38 treatment, stage (International Staging System [ISS]) (I/II or III), with a 55% global enrolment cap for participants with ≤3 prior lines. No cross-over will be allowed until final OS analysis.
 
○ During the Study Treatment Period, safety and disease assessments will be performed regularly according to the schedule of activities (Section 2 of Protocol Amendment 3) for each arm. Participants in both arms will be treated until PD, death, unacceptable toxicity, withdrawal of consent, loss to
 
 
 

Overview of Study Design and Key Features	

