### 5.2. Sample Size Determination

#### Primary Endpoint PFS

Based on available data from literature, the median PFS in the pom/dex arm is expected to be around 4 months [[San Miguel, 2013](#)]. It is expected that treatment with belantamab mafodotin will result in a 43% reduction in the hazard rate for PFS, i.e. an expected HR of 0.57 (corresponding to an increase in median PFS from 4 months to 7 months under the exponential model assumption).

The final PFS analysis will be conducted at the time of observing approximately 151 events and the first 320 randomized subjects have been followed for a minimum of 4 months. With 151 events, the study has a power of 90% to detect a hazard ratio of 0.57 at 1-sided alpha of 0.025 (corresponding to a critical value of 0.713 for the hazard ratio). This calculation assumes participants randomized to the two treatment arms in a 2:1 ratio. Assuming that enrolment will continue for approximately 20 months at a uniform rate of 16 participants per month, a total of 320 participants will be randomized in a 2:1 ratio to receive single agent belantamab mafodotin or pom/dex. It is estimated that the targeted 151 PFS events will be observed approximately 23 months after the first participant is randomized based on a lognormal cure rate model ([Chen, 2016](#)). These calculations were made using the software package East 6.5 and a proprietary SAS macro.

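### The main by-arm AE tables are crude percentages over a window that lengthens with treatment, and the planned by-cycle table only partly corrects for unequal exposure

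*SAP*

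**What the plan says.** **AE displays.** Section 4.5.2 opens with "An overview summary of AEs, including counts and percentages of participants with any AE", and the same overview covers grade 3-4 AEs and AEs leading to permanent discontinuation. "Unless otherwise specified, AEs will be summarized by treatment arms". For SAEs, "All SAEs will be tabulated based on the number and percentage of participants who experienced the event". The summary of AEs of grade 3 or higher is by preferred term, and Section 4.5.2.3 tabulates AEs leading to discontinuation.

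**Counting window.** Under Section 6.2.3 an AE is treatment-emergent up to 70 days after study treatment stops, or up to new anti-cancer therapy if that comes first. The rule is the same in both arms.

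**Treatment length.** Section 1.2 states: "Participants in both arms will be treated until PD, death, unacceptable toxicity, withdrawal of consent, loss to" follow-up or end of study. Section 5.2 assumes "an expected HR of 0.57" for PFS, "corresponding to an increase in median PFS from 4 months to 7 months under the exponential model assumption".

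**Displays that touch on time.** Sections 4.5.2 and 4.5.2.1 also plan cumulative incidence by the number of cycles given when the event first appeared (up to 1, 2, 4, 6, 8 or 10, then *Any*) for AEs, SAEs and each AESI. Time to first onset is summarised for each AESI. Section 4.5.1 summarises duration of treatment by arm, but no AE table uses it as a denominator.

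**The concern.** One secondary objective in Section 1.1.1 is safety and tolerability versus pom/dex, so these tables will be read as a comparison even though no AE test is planned. A crude percentage rises both with toxicity and with time at risk. Treatment normally ends at progression, so a drug that delays progression tends to be given, and its AEs counted, for longer. Two arms with the same monthly risk could then show different percentages. The visible text plans no person-time rate and no censored estimate of AE incidence that would let a reader separate the two explanations.

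**Working it through.** **1. The plan's own figure.** Section 4.5.2 contains no number to check, so the design inputs were checked instead. The medians give HR = 4/7 = 0.571. Events for 90% power at HR 0.57, one-sided 0.025, 2:1 allocation: (1.960 + 1.282)² / [(2/3)(1/3)(ln 0.57)²] ≈ 150. With 151 events power is 0.903, and the critical HR is exp(−1.960/√(151 × 2/9)) = 0.713. The SAP's claim, "With 151 events, the study has a power of 90% to detect a hazard ratio of 0.57 at 1-sided alpha of 0.025", reproduces.

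**2. Time at risk.** *Assumption:* treatment time is exponential with median equal to the hypothesised median PFS. The means are 7/ln 2 = 10.10 and 4/ln 2 = 5.77 months. The full 70-day tail is w = 70/30.44 = 2.30 months. The mean window is 12.40 versus 8.07 months, a ratio of 1.54.

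**3. Crude percentage at equal hazard.** *Assumption:* a constant monthly hazard h, the same in both arms. With mean treatment time m, the proportion with an event is

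1 − exp(−h·w) / (1 + h·m).

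For h = 0.10, exp(−0.230) = 0.7945. Belantamab: 1 − 0.7945/2.010 = 60.5%. Pom/dex: 1 − 0.7945/1.577 = 49.6%.

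The data cut was added by simulation: 20 months of uniform accrual (Section 5.2) and a cut at about 25 months (Section 4.7, Table 8). Gaps come from unrounded values.

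| h per month | No cut: belantamab vs pom/dex | Gap (points) | 25-month cut | Gap (points) |
|---|---|---|---|---|
| 0.02 | 20.5% vs 14.4% | 6.2 | 16.1% vs 12.9% | 3.2 |
| 0.05 | 40.8% vs 30.8% | 9.9 | 34.4% vs 28.4% | 6.0 |
| 0.10 | 60.5% vs 49.6% | 10.8 | 54.7% vs 47.1% | 7.6 |

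**4. Sensitivity.**
- A cut at 23 months, the time Section 5.2 gives for 151 PFS events, leaves gaps of 2.7 to 6.6 points.
- New anti-cancer therapy can shorten the tail. With no tail at all and a 25-month cut, the gaps are 3.9, 7.7 and 10.8 points.
- Very common events hardly differ: at h = 1.0, 99.1% versus 98.5% (full tail, no cut).
- Treatment also stops for reasons other than progression. Extra discontinuation on belantamab alone of 1/5.77 − 1/10.10 ≈ 0.074 per month equalises mean exposure, and the gap disappears.

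**5. The by-cycle table.** Section 1.2 gives 21-day cycles for belantamab and 28-day cycles for pom/dex. Six cycles are 126 versus 168 days, and ten are 210 versus 280. With h = 0.10, on-treatment time only, no data cut and all treated participants as denominator (an assumption, since none is stated):

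| Cycles | Belantamab | Pom/dex |
|---|---|---|
| ≤2 | 12.1% | 14.5% |
| ≤6 | 28.2% | 28.5% |
| ≤10 | 37.5% | 33.6% |
| Any | 50.2% | 36.6% |

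At equal hazard, early rows make pom/dex look worse, and *Any* is the crude percentage again.

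**6. Would a rate be enough?** At equal constant hazards, first events per participant-year give a rate ratio of 1.00. At equal but front-loaded hazards (assumed 0.30 per month for 2 months, then 0.01; 70-day tail, 25-month cut) the crude percentages are 48.8% versus 47.8%, but the rates are 113 versus 138 per 100 participant-years, a ratio of 0.82. A rate alone would then wrongly favour belantamab.

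**The case against.** The strongest reply is that the plan does not rely on crude percentages alone. It has by-cycle cumulative incidence for AEs, SAEs and AESIs, day-banded onset for corneal events and thrombocytopenia, and exposure duration by arm. A reader might infer that no display addresses time at risk; the SAP does not support that. The reply stands only in part, because the by-cycle table has unequal cycle lengths, states no denominator or censoring rule, and leaves out grade 3 or higher AEs and AEs leading to discontinuation. The onset summaries have no stated censoring.

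Second, 7 and 4 months are expected median PFS, and the SAP states no expected treatment duration. A reader might infer that belantamab is bound to look worse. That does not follow: toxicity, withdrawal and other reasons also end treatment, and enough of them in one arm removes the gap. This stands, and it makes the size conditional.

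Third, the AE displays are descriptive, some safety text is redacted, and further detail sits in company standards and the Output and Programming Specification, which are not at hand. That is also true. The SAP states nothing false here. The weakness is in the choice of summary for a comparative objective.

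Fourth, exposure-adjusted rates carry their own bias when toxicity is front-loaded. Step 6 confirms this, so a rate should not be the only addition.

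**Conclusion.** The point holds in a limited form. The main comparative AE, SAE and grade 3-4 tables do not separate toxicity from time at risk, and the by-cycle table repairs this only partly. If treatment time follows the hypothesised PFS, equal constant hazards of 0.02 to 0.10 per month put belantamab about 3 to 8 points higher at the 25-month cut, or 6 to 11 with unlimited follow-up. Both ranges assume the full 70-day tail, and a shorter tail would widen the gap somewhat. The hazards and exponential treatment times are assumptions, not SAP figures. With more non-progression discontinuation on belantamab the gap could shrink to nothing, and crude percentages alone would not show which case had occurred.

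**What to change.** Keep the percentages. For any AE, grade 3-4 AEs, SAEs, AEs leading to discontinuation, corneal events and thrombocytopenia, add by arm:

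- **(a) A rate:** participants with a first event per 100 participant-years at risk over the Section 6.2.3 window, with the rate difference and 95% CI, and a note that it assumes a roughly constant hazard.
- **(b) A curve or table:** cumulative incidence of first event on one calendar-time scale for both arms, censored at the end of that window, with death as a competing event. This guards against front-loaded toxicity misleading (a).

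Leave infusion-related reactions out of both, since Section 1.2 describes pom/dex as oral. State the denominator of the by-cycle table and note its unequal cycle lengths. The cost is a few extra tables from AE, exposure and death dates already collected.

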### **4.5.1. Extent of Exposure**

#### **Belantamab mafodotin Arm:**

Extent of exposure to belantamab mafodotin will be summarized.

The number of cycles administered by study treatment will be summarized with mean, median, standard deviation, minimum, and maximum.

The dose intensity (mg/kg/3 weeks), which is calculated as the cumulative actual dose (mg/kg) divided by expected duration of exposure in 3 weeks [(last infusion date – first infusion date+21)/21], will also be summarized. A by subject summary listing of data on exposure to all study treatments will be produced.

The dose intensity (mg/kg/3 weeks) up to a cycle or infusion except the last (cycle or infusion), which is calculated as cumulative actual dose (mg/kg) up to the current cycle, divided by expected duration of exposure up to the current cycle in 3 weeks [(next

infusion date-1 – first infusion date+1)/21], will also be summarized. The dose intensity up to the last cycle or infusion will be calculated in the same way as the dose intensity earlier.

The duration of exposure to study treatment (from first day to last day of treatment) will be calculated and summarized using mean, median, standard deviation, minimum, and maximum. A horizontal bar graph of duration of treatment will be produced that displays duration of treatment in months for each participant.

Dose reductions will be summarized by number of reductions and reasons for reductions. Dose delays will be summarized by number of delays, reasons for the delays, and delay duration (days). The number and percentage of the delays for intervals of 1-21, 22-42 and >42 days will be computed. Primary reasons for dose reductions and dose delays will also be summarized by cycle.

Duration of delays is defined as period from the expected start date of dose to actual start date of current dose. Calculation: (actual start date of current dose - expected start date of dose). Expected start date of dose = actual start date of previous dose + 21.

The summaries of dose modifications will be provided. All the dose reductions, dose escalations, infusion interruptions, incomplete infusions and dose delays will be listed. A plot showing the number and percentage of participants treated at different dose levels over time will be provided.

A patient profile plot will also be produced of all responders (PR or better based on investigator-assessed response) with any dose delays >63 days.

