#### **Pomalidomide / Dexamethasone Arm:**

The start date of the overall study treatment is defined as the first dose date of pomalidomide or dexamethasone, whichever is earlier (i.e. the first study drug start date). For pom/dex arm, for each cycle, the cycle start date is defined as the pomalidomide start date; the day before the start date of the current cycle (after the 1st cycle) is defined as the end day of the previous cycle. The end date of the last cycle will be calculated as the earliest of: start date of last treatment cycle + 27 days, treatment discontinuation date, which is the date of the last dose, or the death date if the subject discontinues study or dies before the expected end of the last cycle (start date of last treatment cycle + 27 days).

The overall study treatment end date is defined as the end date of the last cycle. The overall treatment duration (days) is defined as:

Overall treatment duration (days)=the overall study treatment end date – the first study drug start date + 1

Separately for pomalidomide and dexamethasone:

- Duration of treatment = the end date of the last cycle of the study drug – the first dose date of the study drug+1
- Cumulative dose = sum of all actual doses taken across the treatment.

- Dose exposure = total number of days on the study drug during the treatment phase, periods of dose break per protocol or dose interruptions will be excluded
- Average daily dose = cumulative dose / dose exposure (mg/day).
- Dose intensity = cumulative dose / duration of treatment (mg/day).
- Relative dose intensity = dose intensity / plan dose intensity:
  - planned dose intensity for pomalidomide =  $4\text{mg} \times 21/28$  days;
  - planned dose intensity for dexamethasone (for participants  $\leq 75$  years old) =  $40\text{mg} \times 4/28$  days;
  - planned dose intensity for dexamethasone (for participants with  $>75$  years old) =  $20\text{mg} \times 4/28$  days;

Descriptive statistics of cumulative dose, dose exposure, average daily doses, dose intensity and relative dose intensity will be summarized by cycle and by pomalidomide and dexamethasone, separately. The overall summary across cycles will also be provided. Duration of treatment by drug and overall treatment duration will be summarized by descriptive statistics.

The dose modifications (dose reductions, dose interruptions) will be summarized by study drug and listed.

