level for the maximum grade, i.e. a participant will only be counted once as the worst case from all the events experienced by the participant. For action taken to an event, a participant will be counted once under each action, e.g. if a participant has an event leading to both study intervention discontinuation and dose reduction, the participants will be counted once under both actions.

An overview summary of corneal events (CTCAE), including counts and percentages of participants with any AE, AEs related to study intervention, Grade 3 and 4 AEs, Grade 3 and 4 AEs related to study intervention, AEs leading to permanent discontinuation of study intervention, study intervention related AEs leading to permanent discontinuation of study intervention, AE leading to dose reductions, AEs leading to dose delays, SAEs, SAEs related to study intervention will be produced. Unless otherwise specified, AEs will be summarized by treatment arms. AEs related to pomalidomide and dexamethasone separately, OR pomalidomide and dexamethasone in combo will all be considered as AEs related to the pom/dex regimen and summarized under the pom/dex treatment arm.

For each of these AESI, a summary of cumulative incidence by number of cycles ( $\leq 1$ ,  $\leq 2$ ,  $\leq 4$ ,  $\leq 6$ ,  $\leq 8$ ,  $\leq 10$ , Any) received at first occurrence will be provided.

For thrombocytopenia, number and percentage of participants with grade 3 or 4 platelet count decreased (based on lab data) and concomitant grade 2 or above bleeding event will be summarized. A bleeding event will be considered as concomitant only if the start date is within  $\pm 3$  days of the lab event.

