#### **4.5.2.3. Adverse Events Leading to Discontinuation of Study Treatment and Other Significant Adverse Events**

The following categories of AEs will be summarized separately in descending order of total incidence by PT only and separate supportive listings will be generated with participant level details for those participants:

- AEs leading to permanent discontinuation of study treatment
- AEs leading to dose delays
- AEs leading to dose interruptions
- AEs leading to dose reductions

Only listings will be provided for the following:

- AEs leading to infusion stopped early and not completed
- AEs leading to infusion interrupted but completed

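### The by-arm AE overviews have a row for dose delays, which the SAP defines only for belantamab mafodotin, and no row for dose interruptions, the category it uses for pom/dex

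*SAP*

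**What the plan says.** SAP 4.5.2 plans an overview table of participants with AEs. Among its rows it names "AE leading to dose reductions, AEs leading to dose delays, SAEs, SAEs related to study intervention, fatal SAEs", alongside permanent discontinuation. Dose interruptions are not named. The same section sets the layout: "Unless otherwise specified, AEs will be summarized by treatment arms".

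SAP 4.5.2.1 plans a second overview, for corneal events on the CTCAE scale, with the same rows on dose modification: "AE leading to dose reductions, AEs leading to dose delays, SAEs, SAEs related to study intervention will be produced". Again there is no interruption row.

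SAP 4.5.1 describes exposure separately by arm:

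- **Belantamab mafodotin.** A delay is measured against the scheduled infusion date: "Expected start date of dose = actual start date of previous dose + 21". The listings are also specified: "All the dose reductions, dose escalations, infusion interruptions, incomplete infusions and dose delays will be listed".
- **Pom/dex.** "The dose modifications (dose reductions, dose interruptions) will be summarized by study drug and listed". Delays are neither named nor defined for this arm.

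SAP 4.5.2.3 plans separate summaries by preferred term, with participant-level listings, for AEs leading to discontinuation, delays and reductions, and also for "AEs leading to dose interruptions".

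**The concern.** Withholding a drug for toxicity takes different forms in the two arms. For an infusion given every 3 weeks, it appears as a late infusion. For pomalidomide taken on Days 1 to 21 of a 28-day cycle with weekly dexamethasone, it can appear as missed doses within a cycle. The SAP's exposure section reflects this by using delay for one arm and interruption for the other.

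The overviews keep only the first term. A reader comparing the arms on that row would take it as the frequency with which AEs caused dosing to be held. For pom/dex it may cover only some of those holds. The overview is where readers first compare tolerability, and this is an open-label trial whose safety comparison is descriptive. A row that means different things in the two columns is therefore easily misread.

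**Working it through.** No arithmetic applies. The SAP states no rate of delays or interruptions and no figure that could be reproduced, so the check sets the sections side by side.

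| Place in SAP | Delay | Interruption |
|---|---|---|
| 4.5.1, belantamab mafodotin | Defined and summarised | Infusion interruptions listed |
| 4.5.1, pom/dex | Not named or defined | Summarised by study drug and listed |
| 4.5.2, AE overview by arm | Row | No row |
| 4.5.2.1, corneal-event overview | Row | No row |
| 4.5.2.3, AE tables by preferred term | Separate table | Separate table |

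1. **Is a delay defined for pom/dex?** No. The definition in 4.5.1 counts from the previous dose plus 21 days, and it stands under the belantamab mafodotin heading. It cannot be carried over to a drug taken daily or weekly within a 28-day cycle. The other place that fixes the onset of a delay is the KVA-scale analysis in 4.5.3.2, and that display is also restricted to the belantamab mafodotin arm.

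2. **Does the SAP treat the two terms as one?** No. 4.5.2.3 names delays and interruptions as separate categories with separate tables. It handles infusions that were interrupted but completed, or stopped early, in listings only. Dose interruption is therefore not just another name for infusion interruption.

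3. **Are pom/dex interruptions reported anywhere?** Yes. 4.5.2.3 tabulates AEs leading to dose interruptions, and the general rule in 4.5.2 puts that table by arm. 4.5.1 also summarises pom/dex interruptions as exposure data.

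4. **Does any planned summary give participants per arm with any AE-driven hold?** No. The delay and interruption tables are separate. Their participant totals cannot be added, because one participant may appear in both.

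5. **Which way would the overview row err?** If pom/dex holds are coded mainly as interruptions, the row is too low for the control arm, and belantamab mafodotin looks relatively worse on it. If they are coded mainly as delays, the effect is small. The SAP does not show the coding, so the direction is conditional and the size is unknown.

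**The case against.** The strongest case against the point has four parts.

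- **The events are tabulated elsewhere.** A reader might infer from the overviews that control-arm holds vanish from the safety comparison. The SAP does not support that: 4.5.2.3 gives AEs leading to interruptions their own by-arm table and listings. For corneal events, 4.5.2.1 also plans a summary of action taken, with a participant counted once under each action. This part stands and confines the point to the overviews. It does not supply the combined count, because all of these displays work one category at a time.

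- **The coding is not shown.** A reader might also infer that pom/dex holds are always recorded as interruptions. The pom/dex text in 4.5.1 says how exposure data are summarised, not which actions the eCRF offers when an AE is reported. Since cycles in that arm are dated from the start of pomalidomide, a late cycle start could be recorded as a delay. This stands, so the understatement must be stated conditionally. It is also a reason to define both terms by arm.

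- **The list of rows may not be exhaustive.** The overview rows are introduced as inclusions, and the SAP leaves the specification of displays to the OPS. An interruption row is therefore not barred. That is true, but the SAP names the delay row twice and the interruption row in neither overview, so following it as written gives the unequal comparison.

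- **The holds are not equivalent.** A late 3-weekly infusion and a few missed days of an oral drug differ in weight, so a merged row pools unlike things. This is a fair reason to keep the separate delay and interruption displays beside the combined row. It does not favour a row that may capture the holds of only one arm.

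The union could be counted by hand from the participant-level listings. That shows the data exist; it does not make the listings a planned summary.

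**Conclusion.** The point holds as a reporting inconsistency in two descriptive tables. Both overviews compare the arms on a category the SAP defines for belantamab mafodotin only, and both omit the category it uses for pom/dex, although 4.5.2.3 treats interruptions as worth tabulating. To the extent that pom/dex holds are coded as interruptions, the overview row understates AE-driven holds in the control arm.

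The size cannot be computed from the SAP. It depends on the proportion of each arm with AE-driven holds and on how those holds are coded, and neither is given. The effect on the corneal-event overview is probably minor. PFS, OS and the control of type I error are unaffected. The point is worth correcting because the overview is a headline safety table and the correction is cheap.

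**What to change.** 1. In the overviews of SAP 4.5.2 and 4.5.2.1, add a row for AEs leading to dose interruption or delay (any component), counting each participant once.
2. Keep the separate delay and interruption rows or tables, including those in 4.5.2.3, as supportive displays.
3. State in the SAP or OPS how delay and interruption are derived in each arm. For pom/dex, say whether a hold of either drug counts and whether a late cycle start is a delay or an interruption.

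The cost is a wording change and one derived participant-level flag. The tables in 4.5.2.3 already require both component flags, so no new data are collected. No rule for managing treatment is touched.
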